Group systemic reflective practice is a core part of systemic practice. Studies show that it provides a space for practitioners to reflect on and embed systemic principles into their everyday practice with children and families.⁴⁶ A key principle is that practitioners, managers or clinicians do not hold all the answers about how best to progress work with a family. Instead, solutions develop when working collaboratively. It is different from one-to-one supervision that might occur between a practitioner and manager because the focus is on generating multiple perspectives to consider the family system in a group reflective space. Sessions can involve case presentations, group discussions, role-play, and testing of different tools and techniques learned in training. The frequency and make-up of the sessions (for example being in whole teams or smaller groups) can vary.

An example of how group-based reflective sessions take place in one local authority is set out below.

Practice meetings are held weekly and are chaired by a Unit Leader or in their absence, a designated senior-level practitioner. All members of the Unit are expected to be present at every meeting. Families are discussed at least once within a four-week cycle. All attendees are expected to prepare for Practice Meetings by thinking about the cases for discussion and noting the information they will bring. For new cases, attendees are expected to read key documents. During practice meetings, discussions about each case cover:

- A review and update of family or individual plans
- Sharing information about needs of children and family dynamics
- Risk management

⁴⁵ AFT. Training route for family and systemic psychotherapy and development of systemic. Available at: practice <https://www.aft.org.uk/page/routestoqualification>

⁴⁶ Bostock, L., Patrizio, L., Godfrey, T., & Forrester, D. (2022). Why does systemic supervision support practitioners' practice more effectively with children and families? Children and Youth Services Review, 142, 106652. <https://doi.org/10.1016/j.chlyouth.2022.106652>

- Problem-solving and generation of creative solutions
- Sharing information about unit performance.

Source: Royal Borough of Greenwich's Early Help Operating Guidance

Systemic practitioners will lead the sessions as evidence suggests that having a qualified practitioner trained in systemic practice attend is important to ensure the full incorporation of systemic concepts and practice in the supervision.⁴⁷

Systemic tools

Systemic tools such as genograms, ecomaps and family trees are an important part of systemic practice. They give a pictorial representation of a family system including ages, relationships, life events etc.⁴⁸ and although often led by a practitioner, are meant to be developed in collaboration with the family. They can be used to identify patterns of relationship, historical influences and stressors on the family, and to consider how these may impact on the problem/difficulty being experienced by the individual or family.

They can be used at any stage of a family's interaction with practitioners and revisited and updated but are often created during initial visits and in the assessments phase. They can be utilised for the practical purposes of information gathering on families, but also as part of the therapeutic process.⁴⁹

These systemic tools form a central part of systemic supervision and genograms were one of eight features described for a unit meeting to be considered systemic in a study comparing systemic practice to service as usual.⁵⁰

Another systemic tool is the SCORE-15, a measure used to assess family functioning and will be both a secondary outcome measure (see below) and used as part of the therapeutic process as a tool to understand the family and develop a therapeutic alliance, as well as provide avenues for the family to explore their own relationships and dynamics.

⁴⁷ Bostock, L., Forrester, D., Patrizo, L., Godfrey, T., Zounouzi, M., Antonopoulou, V., ... & Tinarwo, M. (2017). *Scaling and deepening the Reclaiming Social Work model*. Department for Education. https://assets.publishing.service.gov.uk/government/uploads/system/uploads/attachment_data/file/625227/Scaling_and_deepening_the_Reclaiming_Social_Work_model.pdf

⁴⁸ Research in Practice (2019). *Drawing a genogram*. <https://practice-supervisors.rip.org.uk/wp-content/uploads/2019/11/Drawing-a-genogram.pdf>

⁴⁹ Research in Practice (2021). *Using genograms in practice*. https://www.researchinpractice.org.uk/media/4962/cf_pt_using-genograms-in-practice_final.pdf

⁵⁰ Bostock, L., Forrester, D., Patrizo, L., Godfrey, T., Zounouzi, M., Antonopoulou, V., ... & Tinarwo, M. (2017). *Scaling and deepening the Reclaiming Social Work model*. Department for Education. https://assets.publishing.service.gov.uk/government/uploads/system/uploads/attachment_data/file/625227/Scaling_and_deepening_the_Reclaiming_Social_Work_model.pdf

Incentives for control local authorities

To ensure recruitment and retention of control local authorities throughout, online introductory sessions for key workers, senior leaders and managers will be provided at the start of the pilot, providing an overview of what it means to be in the control group, including training in administering family outcome measures and an explanation of the training they will receive after the pilot delivery. Control group local authorities will also be given a financial grant to support data collection, along with ongoing support from the evaluation team to troubleshoot queries, concerns or issues.

As a further incentive, at the end of pilot delivery, IFT will deliver CPD certified 2 days' training to keyworkers to provide an overview of systemic practice, including ways to embed it within practice using tools and techniques supported by worked examples, observations and reflection sessions.

Impact evaluation

Research questions

As highlighted above, the pilot study has two primary aims: (i) to provide indicative evidence of the impact and efficacy the model delivers on family outcomes compared to models that do not use this specific approach, and; (ii) to establish the feasibility of delivering a full trial of the model.

The impact evaluation has one primary research question:

1. Do families who have a keyworker have **improved progress towards personal goals** in line with the Supporting Families Outcomes in local authorities that have implemented systemic practice compared to local authorities that have not?

This is supplemented by six secondary research questions:

1. Do families who have a keyworker have **increased levels of family functioning** in local authorities that have implemented the systemic practice model compared to local authorities that have not?
2. Do families who have a keyworker have a **better therapeutic alliance with their keyworker** in local authorities that have implemented systemic practice compared to local authorities that have not?
3. Are there **reductions in step-up to statutory support** for families with a keyworker in local authorities that have implemented systemic practice compared to local authorities that have not?
4. Are there **more case closures with positive progress** made by families who have a keyworker in local authorities that have implemented systemic practice compared to local authorities that have not?
5. Do keyworkers in local authorities that have implemented systemic practice have **increased levels of professional wellbeing** compared to keyworkers in local authorities that have not?
6. Do keyworkers in local authorities that have implemented systemic practice have **improved practice quality** compared to keyworkers in local authorities that have not?

Design

The study will use a parallel 1:1 randomised controlled trial design to compare business-as-usual to business-as-usual plus embedded systemic practice. The local authorities in the sample have in common the fact that they currently, or in the last three years, have not implemented systemic practice throughout their keyworker teams. Business-as-usual will be the standard approach to early help/family help as set out in the Supporting Families Programme guidance.⁵¹

Table 1: Systemic practice trial design

| | |
|---|---|
| Trial design, including number of arms | Parallel non-blinded trial 1:1 randomisation |
| Unit of randomisation | Local authority |
| Stratification variables (if applicable) | Local authority structure |
| Primary outcome | Variable: Progress towards personal goals within the Supporting Families Outcome Framework Measure(s) (instrument, scale, source): Goal Based Outcomes (GBO) |

⁵¹ Department for Education and Department for Levelling Up, Housing and Communities. Supporting Families Programme guidance 2022 to 2025: Guidance. <https://www.gov.uk/government/publications/supporting-families-programme-guidance-2022-to-2025>

| | |
|---------------------------------------|--|
| Secondary outcome(s) | 
Variable(s):
 
 1. Family functioning 2. Therapeutic alliance 3. Step-up to children's social care 4. Positive progress made by families 5. Professional wellbeing 6. Quality of practice 
Measure(s) (instrument, scale, source):
 
 1. SCORE-15 Index of Family Functioning and Change 2. The Consultation and Relational Empathy (CARE) measure 3. Outcome at closure – Early Help dataset 4. Outcome at closure – Early Help dataset 5. An adapted measure of professional wellbeing 6. An adapted measure of systemic practice quality |
| Baseline for primary outcome | 
Variable: Progress towards personal goals
 
Measure(s) (instrument, scale, source): Goal Based Outcomes (GBO)
 |
| Baseline for secondary outcome | 
Variable(s):
 
 1. Family functioning 2. Therapeutic alliance 3. [None] 4. [None] 5. Professional wellbeing 6. Quality of practice 
Measure(s) (instrument, scale, source):
 
 1. SCORE-15 Index of Family Functioning and Change 2. The Consultation and Relational Empathy (CARE) measure 3. [None] 4. [None] 5. An adapted measure of professional wellbeing 6. An adapted measure of systemic practice quality |

Randomisation and blinding

The unit of randomisation is at the local authority level. We have randomised at a local authority level for two main reasons:

- Contagion effects at a keyworker, or family level. The practice model is a whole service approach which would be difficult to implement if randomisation took place either at a team, keyworker, or family level. This was a key concern in Foundation's Rotherham pilot study which could have contributed to its limited effects.⁵²
- Ethical considerations. Having received initial advice from Coram's Research Ethics Committee, ethical issues were identified in a trial that provided psychologically informed keyworker practice to some families and not others within the same service as the support families would receive could be very different. There may also be a tendency to prioritise families receiving support from systemically trained keyworkers.

As is typical of trials in the field of social policy, the trial is unblinded. Keyworkers and families will know they are part of a pilot study. Keyworkers will be notified when undertaking training as part of the pilot. Families will be told when they are asked to consent to taking part in the pilot study. This lack of blinding is a necessity of the trial design. However, we have selected standardised self-reported outcomes and routinely collected early help data for family outcomes to avoid observer bias that may be introduced if outcomes were to be assessed by unblinded keyworkers for example.

In early discussions, local authority structure, size of Free School Meals population, and rate of Children in Need were identified as some of the possible variables that could be used to stratify and randomise the local authorities signing up to the Supporting Families trial. All three of these alternatives were examined to establish what approach might work best to provide an equitable distribution of families and key workers supporting across the two trial arms. Based on this randomisation will be stratified by local authority structure.

The randomisation procedure by LA structure was be carried out using a combination of random allocation rules to ensure equal arm allocation (control = 0, intervention = 1). The random allocation rules were generated in the statistical package R for each local authority and were combined in Excel to carry out the randomisation. To make the distribution more equitable, a special allocation procedure was used for local authority

⁵² Burridge, H., Nolan, J., & Stanford, M. (2023) Piloting the implementation of systemic training and feedback tools in Rotherham's Early Help & Family Engagement Service: Evaluation report. <https://www.eif.org.uk/files/pdf/piloting-implementation-systemic-training-feedback-tools-rotherham-early-help-family-engagement.pdf>

structures with uneven numbers, utilising the number of families supported as set out in local authority expressions of interest for the pilot. This included:

- Randomly allocate County Councils to each trial arm.
- The arm being allocated with the County Council serving more families (compared to the other County Council) was allocated the Metropolitan Council serving fewer families (compared to the other Metropolitan Council), and the trial arm with the County Council serving fewer families was allocated the Metropolitan Council serving more families compared to the other Metropolitan Council.
- The arm being allocated with the County Council serving more families was allocated the London Borough serving most families, as well as the Unitary authority serving the least families. The other two London boroughs were allocated to the other trial arm.
- The remaining Unitary authorities were allocated randomly across trial arms.

While this process was not completely random, it did guarantee a more equitable split of the sample across the two trial arms. For comparison, we simulated three processes completely at random, to see how the allocations vary across trial arms. To test the performance of the approaches, 100 simulations of each randomisation were conducted to compare the variation of the gap between arm allocations. As was expected, the more deterministic approaches have a smaller gap in the number of families between trial arms, while the more random approaches have bigger gaps. While the minimum gaps are smaller in the more random approaches, they occur with very low probabilities (~ 5%), with the overall approach having a larger variation.

The approach set out above was used to ensure an equitable distribution of families. This approach also ensured a more equitable distribution of the keyworker sample across arms. To strengthen the validity of the approach further, baseline equivalence testing⁵³ of possible allocations across trial arms was carried out against relevant covariates⁵⁴ to examine any possible bias emerging within trial arms. There was no significant difference between the covariates across the two arms in any of the scenarios (alpha = 0.05).

In addition, those undertaking the trial analysis will be blinded to randomisation. We will prepare the main analytical dataset so that trial arm is indicated by numbers and there is no data about participation in the pilot trial (i.e. the data analyst cannot infer which

⁵³ A two-tailed t-test between the means of two independent samples with unequal variances was conducted for each of the covariates across trial arms, with standard assumptions (alpha = 0.05). The Wilcoxon Test was also used for a portion of the cases to verify these results.

⁵⁴ The covariates examined at Local Authority Level were: Proportion of Child Population (0-18) (2022 Mid-Year Estimates); Share of Population known to be eligible for Free School Meals (2022-23); Proportion of Children in Need (2023); Proportion of School Children Requiring SEN Support (2022-23); Proportion of Children Looked After (2023); Proportion of Children in Low Income Families (2022-23). For Westmorland and Furness, the data for Cumbria (the LA that contained it previously before it split on 01 April 2023) was used.

participants received the intervention and which did not). This, in addition to the a priori data analysis plan, will prevent bias being introduced during data analysis.

Participants

The trial aimed to recruit twelve local authorities to take part in the pilot, six intervention local authorities embedding systemic practice in keyworker teams, and six local authorities not embedding systemic practice.

Keyworkers will be practitioners working in local authorities' family support or early help services (including those in the Supporting Families Programme) providing support to a caseload of families within the timeframe of the pilot.

Participants will be families (parents/carers and their children/young people aged 8 and over) that meet the following criteria:

- A parent/carer who has a keyworker within the trial period. This will mainly include 'new' families; those that are referred and then supported by a keyworker within the pilot period. Keyworkers will have to work with a family for at least 10 weeks within the pilot period, as we want to evaluate families with ongoing contact with this service that would be expected to be influenced by the treatment.
- Parent/carer has one or more children aged 0-17 they have legal responsibility for at the point of referral.
- Child or young person 8 years old and over as outcome measures have not been adapt for children younger than 8 years old.

Exclusion criteria

Local authorities were not eligible for the pilot if they:

- Currently, or in the last three years, have implemented systemic practice in their keyworker teams. This includes systematic training in systemic practice for keyworker or the hiring/commissioning of Psychotherapists or Clinicians to support keyworkers.
- Were initial Families First for Children DfE pathfinder local authority; or
- Currently, or in the last two years, have an inadequate Children's Services Ofsted rating.

Recruitment

Local authorities were recruited via an Expression of Interest (EOI) hosted on Coram's website. The EOI was advertised through a number of routes including a press release from Coram, IFT and Ecorys, several sector press articles as well as a number of notices including by ADCS and in the DfE DCS newsletter. In addition, the then Supporting Families Programme hosted a webinar and posted repeatedly on their weekly newsletter. The Programme also advertised it through their local authority development team and via DfE's social care regional programme advisors.

Coram assessed the EOIs and then undertook randomisation of 12 local authorities. Since randomisation occurred, two local authorities in the control arm have dropped out of the trial, resulting in a total sample of ten local authorities, six in the intervention arm and four in the control arm.

Reasons for dropout included limited capacity for additional data collection and decisions to implement systemic practice and training in the local authority in the pilot period. One of the local authorities was embarking on a new framework and practice standards which included systemic principles alongside a wider change programme within the local authority which limited their capacity to implement new approaches to outcome collection with families. The other local authority also wished to implement systemic practice within the pilot period. They also noted that the required additional data collection would be too burdensome on staff and family time and require additional resources to oversee and quality assure the processes, particularly as they would have fell outside their current established measurement system already in place.

Within the pilot local authorities, all keyworkers in both control and intervention local authorities will take part in the study.

Recruitment of families into the pilot study has the advantage of being determined by eligibility for support by keyworkers. As a result, all families supported by a keyworker within the trial period will be eligible to be included within the trial if they consent to take part when completing the Family Outcome Questionnaire. Keyworkers in both control and intervention local authorities will receive training and detailed guidance in administering the Family Outcome Questionnaire. They will also receive ongoing support from Coram as well as from their local authority systemic practitioner including refresher training and drop-in sessions for troubleshooting.

Sample size calculations

When using a mixture of initial and revised numbers of families supported by local authorities that expressed an interest in the pilot, we decided to consider only 75% of the reported figures in our calculations. Our reasoning behind this was that whilst local

authorities provided their caseloads, we want to be cautious when taking these numbers into our estimates, as the caseload numbers may contain errors or old data, may include inactive or ineligible cases, and may include cases that are inaccessible as part of an evaluation owing to practicalities such as families relocating.

We hence conservatively estimate that the systemic practice trained keyworkers would potentially be dealing with 7,766 families, of which 1,165 families would participate in our programme data collection at baseline. Based on our assumptions on trial attrition in the CONSORT, this would amount to an analysable sample of 560 families, which was used to estimate an MDES of 0.446. While the dropout has led to a potential imbalance between treatment and control (65%:35%), this has been accounted for in our power calculations. We feel that this MDES is sufficient to detect a significant change using the GBO, with studies showing effect sizes^{55,56,57,58,59}

Table 2: Sample size calculations

| Parameter | Value |
|---------------------------------------|--|
| Minimum Detectable Effect Size (MDES) | 0.446 |
| Pre-test/ post-test correlations | Level 1 (participant): 0.6 Level 2 (family): 0.6 Level 3 (LA): 0.6 |
| Intraclass correlations (ICCs) | Level 2 (family): 0.3 Level 3 (LA): 0.1 |
| Alpha | 0.05 |

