This protocol summarises plans for a pilot randomised controlled trial (RCT) and process and implementation evaluation of a pilot to embed systemic practice in keyworker teams as part of the Department for Education's Supporting Families Programme. The aims of the pilot trial are to:

1. Provide indicative evidence of the impact and efficacy that the model delivers on family outcomes compared to models that have not embedded systemic practice in their keyworker teams, and;
2. Establish the feasibility of delivering a full trial of the model in a larger number of local authorities.

A consortium led by Coram and the Institute of Family Therapy (IFT) will deliver the pilot. Twelve local authorities submitted Expressions of Interest (EOIs) and entered the randomisation process, six were randomised into the intervention group and six into the control group. Unfortunately, two local authorities in the control group dropped out of the pilot due to capacity and internal transformation projects taking place. The pilot RCT therefore comprises ten local authorities, six in the intervention group and four in the control group.

The pilot began in October 2024 and will end in May 2026. The evaluation is being led by Coram, partnering with Ecorys.

The six intervention group local authorities have begun embedding of systemic practice. This has included training in systemic practice to keyworkers by IFT, the hiring of systemic practitioner by local authorities and on-going support via a virtual systemic practice hub run by IFT and IFT's Systemic Psychotherapist Delivery Lead. The four control group local authorities not embedding systemic practice in the pilot period are being provided with technical support to collect data throughout the pilot and will receive training in systemic practice at the end of the trial period.

Findings will inform the development of the Families First Partnership programme delivery and wider children's social care policy, including the Government's reform of children's social care.

Background and previous evidence

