| Number of families ⁶⁰ | Intervention: 361 Control: 199 Total: 560 |
| Number of participants | Intervention: 369 adults, 193 children Control: 203 adults, 101 children Total: 572 adults, 294 children |

⁶⁰ Final numbers reported (post attrition) that we will be analysing, rather than in the entire sample.

Updated sampling calculation (LAs = 10) – Only SF sample and latest assumptions

[figure not shown]

Figure 3 – Sampling calculations

SF Sample Size Calculation Table

| | |
|--------------------------------|------------|
| MDES | 0.446 |
| Alpha Level (α) | 0.05 |
| Two-tailed or One-tailed Test? | Two-tailed |
| Power (1- β) | 0.8 |
| Baseline/Endline correlations | |
| Individuals | 0.6 |
| Families | 0.6 |
| Local authorities | 0.6 |
| Average cluster size | |
| Individuals in families | 1.5 |
| Families in local authorities | 56 |
| Number of local authorities | 10 |
| Intraclass cluster correlation | |
| Families | 0.3 |
| Local authorities | 0.1 |

Assumptions

- 3 level clustering – individual in family in local authority
- Assumed a low ICC for families in terms of family functioning (expect different views)
- Assumed a very low ICC for local authorities in terms of family functioning (some clustering of scores based on shared factors, but not strong)
- Assumed baseline/endline correlations of 0.6 at all levels (unknown)

Figure 4 – SF Sample size calculation table

Outcome measures

Table 3: Primary outcome measures

| Variable | Progress towards personal goals |
|------------|--|
| Measure | Goal Based Outcomes (GBO) ⁶¹ |
| Sample | Parents/carers and children/young people aged 8 and over. The GBO will be administered as part of the Family Outcome Questionnaire at an individual level by keyworkers. There will be an adult version (for use with adults and young people aged over 12) and a child-friendly version (for use with children aged 8 to 12). Total GBO scores will be reported, as well as themed scores. We anticipate theming goals using existing taxonomies from psychotherapy research ^{62,63} and using inductive analysis owing to the novel context for use of the GBO. |
| Time point | Baseline: within the assessment period of the first six weeks of the keyworker working with a family. Midline: at a review point when working with the family. Typically, this is between two to five months of working with the family. Endline: At closure when the keyworker stops working with a family. |

Secondary outcome measures for families:

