Eligibility for the pilot study also has the advantage of being determined by eligibility for support by keyworkers meaning that all families supported by a keyworker will be eligible to be included within the trial, if they consent to take part when completing the Family Outcomes Questionnaire. For families that do not consent to take part in the trial, we will request aggregate level anonymous data about these families from local authority case management administrative data. This will allow us to compare the characteristics of those who do and do not consent to the trial. This will include potential biases across characteristics such as type of need at referral, whether they are being re-referred as well as demographic characteristics such as, sex, race and ethnicity, and disability.

Coram was responsible for randomisation and undertook internal quality assurance checks to minimise any biases.

Coram will also explore the influence of trial arm allocation compliance using Complier Average Causal Effect Analysis (meaning whether families or keyworkers in the intervention arm receive the intervention), by including intervention receipt in an instrumental variable analysis. Keyworkers in the intervention arm that attend at least 80% percent (four out of five days) of the initial five-day systemic practice training for all keyworkers will be deemed compliant. This threshold of 80% was recommended by IFT based on their extensive experience of keyworkers being able to use and embed systemic training in their practice. IFT and the local authorities will record attendance of keyworker training which will be included in the administrative data collected.

Quality assurance of the Family Outcome Questionnaire data will be undertaken frequently, and any missing, anomalous or any potential biases in the data will be queried with the respective local authority. If any consistent issues are identified, additional guidance and targeted training for keyworkers and additional guidance within the questionnaire for families will be provided to help ensure compliance.

Implementation fidelity will be measured according to the core components of the systemic practice pilot. This is set out in the table below.

Table 10: Implementation fidelity measures for intervention local authorities

| Component of fidelity | Measure | Source |
|--------------------------------------|---|---|

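### Analyst blinding cannot work as described: with six intervention and four control local authorities, coding the arm by number does not hide it

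*Protocol*

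**What the plan says.** Under Randomisation and blinding, the protocol states that "those undertaking the trial analysis will be blinded to randomisation". The mechanism follows: "We will prepare the main analytical dataset so that trial arm is indicated by numbers". The same dataset is to leave out any record of who took part in the pilot. The protocol explains in brackets that the analyst will then be unable to work out who had the intervention. It concludes: "This, in addition to the a priori data analysis plan, will prevent bias being introduced during data analysis".

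Elsewhere the protocol makes the arms distinguishable. The opening summary says: "The pilot RCT therefore comprises ten local authorities, six in the intervention group and four in the control group". The Recruitment section repeats the 6 v 4 split and explains that both withdrawals were from control. Table 2 projects the analysable families as "Intervention: 361 Control: 199 Total: 560". The impact-evaluation Analysis section plans a three-level model for family outcomes, with terms for delivery site, adjustment for the stratification factor (LA structure) and reported ICCs.

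**The concern.** Masking an analyst by recoding the arm works only if nothing else in the file separates the two codes. Here the arms differ in a feature that the model cannot do without, the number of clusters, and the protocol publishes which arm has more.

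What is at stake is the set of decisions that could be taken after data are in hand. The Analysis section adjusts for characteristics found significantly unbalanced between arms, lets the assessment of missing data change the approach, leaves multiple imputation to be considered, and mentions exploratory subgroups without naming them. The section on the primary outcome measure adds themes generated inductively from the goals that families set. If such choices are made by someone who can tell the arms apart, they can drift towards a favourable result without intent, while the final report describes the analysis as blinded. Families and keyworkers are unblinded and the family questionnaire is self-reported, so analyst masking would be one of few remaining protections if it worked.

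**Working it through.** **1. The plan's own split.** From Table 2:
- 361 + 199 = 560 families.
- 361/560 = 64.5% intervention; 199/560 = 35.5% control.

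This agrees, to about half a percentage point, with the 65%:35% given under Sample size calculations. These are projections after assumed attrition, not achieved counts.

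**2. LA counts (the decisive step).** Inputs: 6 intervention and 4 control LAs (opening summary, Recruitment); an LA identifier in the dataset (needed for the LA level and site terms in the Analysis section). Each LA belongs to one arm only. Tabulating distinct LA identifiers by arm code therefore gives 6 under one code and 4 under the other. As 6 ≠ 4, the code with six is the intervention, whether the codes are 0/1, 1/2 or anything else, and whether or not LA names are removed. No outcome data are needed. With the twelve LAs first randomised, 6 v 6, the count alone would not have separated the codes; the loss of two control LAs is what makes it do so.

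The assumption is that all ten LAs contribute data. The count would fail only if further losses brought the arms level, for example 4 v 4.

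**3. Family totals without LA identifiers.** These are weaker evidence. Assume that family numbers per LA follow a log-normal distribution with the same mean in every LA, and simulate 200,000 sets of ten LAs. The coefficient of variation (CV) is not in the protocol, so a range is shown.

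| Assumed CV of families per LA | Probability that the six-LA arm has more families |
|---|---|
| 0.2 | 0.999 |
| 0.4 | 0.95 |
| 0.6 | 0.87 |
| 0.8 | 0.81 |

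The larger arm is probably the intervention, but not certainly.

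**4. Other possible routes.**
- The 0/1 coding appears in the description of the allocation rules, used to "ensure equal arm allocation (control = 0, intervention = 1"). Nothing says that the analysis file keeps these values.
- On training attendance, the Compliance and fidelity section says: "IFT and the local authorities will record attendance of keyworker training which will be included in the administrative data collected". It is needed for the complier analysis, but the blinding paragraph keeps participation data out of the main dataset. It reveals the arm only to an analyst who handles it before the main analysis is finished.
- The evaluation lead carried out the randomisation (Compliance and fidelity) and is also listed for data cleaning and outcome analysis (Annex A). This shows exposure of the organisation, not that a given analyst knows the allocation.

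Step 2 is sufficient without any of these.

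**The case against.** The strongest reply is that this is a narrow fault of wording. The section names two protections, and the second, an a priori plan, does not depend on masking. The Analysis section promises a final statistical analysis plan before any analysis, second-person checking of code, and publication of the code. That plan is not among the documents reviewed and may settle every choice listed above. All of this stands, and it limits the point to the masking claim.

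A reader might infer four stronger things, and the protocol supports none of them:

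- *That there is no protection against analysis bias at all.* The a priori plan remains; only the masking fails.
- *That the published 0/1 codes give the arm away.* They are documented for the randomisation step only.
- *That 361 v 199 identifies the arm at once.* These are projected numbers, and family totals alone leave real doubt if LAs vary much in size.
- *That attendance records or LA-by-LA data queries unblind the analyst.* Attendance is excluded from the main dataset, and the protocol does not say that the person raising queries is the analyst.

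The reply fails on one matter. The protocol does not say that masking is partial or desirable; it says the analyst will be unable to infer the arm. That is contradicted by the protocol's own LA counts and its own model.

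**Conclusion.** The point holds in limited form. The analyst-blinding statement cannot be met as described: anyone with the arm code and the LA identifier can name the intervention arm with certainty from the 6 v 4 count. This rests on two assumptions, that the analysis file carries an LA identifier, which the planned model requires, and that all ten LAs supply data. The masking component is ineffective, so protection against bias in the analysis rests on the a priori plan. The size or direction of any bias cannot be estimated from the protocol, and there is no evidence that any has occurred. The sample size, detectable effect and type I error rate are unaffected. A correction is worth making because the final report could otherwise claim a blinded analysis that did not take place.

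**What to change.** Adopt one of two options and state it in the protocol and the statistical analysis plan.

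**(a) Make the masking work.**
- A team member who neither analyses the data nor checks the analysis code holds the key. They supply a dataset with LA names removed and the true arm either withheld or replaced by an arm variable permuted across LAs at 6:4. Permutation succeeds where relabelling fails, because the count then says nothing about the true allocation.
- Cleaning, scoring, goal theming, missing-data rules and model code are completed and locked on that dataset.
- The true arm is then attached once and the locked code is run.
- Covariates triggered by imbalance between arms cannot be chosen on a permuted arm, which would pick up spurious imbalance and miss real imbalance. Either apply the trigger after the true arm is attached, by a mechanical rule written beforehand, or replace it with a pre-specified covariate list.
- The complier analysis, which needs attendance data, is run last.

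**(b) Withdraw the claim.** Delete the statements that the analyst will be unable to infer the arm and that bias will be prevented. Report the analysis as unblinded, and rely on the analysis plan and code being finalised before outcome data by arm are seen.

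**Cost.** Option (b) changes wording and requires the plan and code to be finalised in time. Option (a) needs some extra data preparation and a person kept apart from the analysis; the protocol gives no basis for putting hours on this. Annex A places cleaning in June 2026 and analysis in August 2026, so the locking step would fall between them. Option (a) is also imperfect: with only ten LAs, scrambled identifiers may still be partly recognisable from LA structure and size, and the report should say so.
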